10. Have discontinued all previous therapies for MPNs including ruxolitinib, any chemotherapeutic agents, immunosuppressive therapy (e.g., corticosteroids > 10 mg/day with the noted exception: use of corticosteroids for management of gout is allowed; maintenance supplemental corticosteroid therapy such as prednisone ≤ 10 mg/day or corticosteroid equivalent is allowed), immune modulators (e.g., thalidomide), radiotherapy for at least 2 weeks prior, and interferon for 4 weeks prior to study Day 0. Low dose acetylsalicylic acid is permitted. Palliative radiation treatment to non-index or bone lesions performed < 2 weeks before treatment may be considered with Medical Monitor approval.
11. Amenable to bone marrow evaluation, peripheral blood and urine sampling during the study.
12. Able to swallow capsules.

13. Women of childbearing potential (WOCBP) and fertile men (see Section 6.1) must agree to use an approved method of contraception from Screening until 28 days\* after last IMG-7289 dose. Methods of contraception include: estrogen and progestogen combined hormonal contraception which inhibits ovulation; progestogen-only hormonal contraception associated with inhibition of ovulation; intrauterine device (IUD); bilateral tubal occlusion; vasectomized partner in a monogamous sexual relationship (vasectomy or tubal ligation at least six months prior to dosing); and, complete sexual abstinence (defined as refraining from heterosexual intercourse). Patients practicing abstinence must agree to use an approved method of contraception should they become sexually active during the study.

**Note:** In the UK, males with a pregnant partner must agree to use a condom to avoid exposure to the developing child.

\* The risk of embryofetal toxicity is fully mitigated by 28 days which is >10 half-lives of the drug at the doses used in this study.

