The analyses described in this plan are considered *a priori*, in that they have been defined prior to database lock. If any post-hoc analyses are performed, they will be defined and reported in the CSR.

All analyses will be performed using SAS statistical analysis software version 9.4 or higher of SAS for Windows [SAS Institute Inc; Cary, NC, USA]).

A. Data Sources

All data are collected *via* electronic case report forms (eCRFs) through remote data entry. Section 13.6 of the protocol describes data quality assurance.

B. Definition of Baseline

For analysis purposes, baseline is defined as the last assessment prior to the first dose of study drug. Day 0 is the first day a patient receives study drug. For most measurements, baseline assessments will be taken pre-dose on Initial Treatment Period ITP Day 0. If pre-dose assessments on Day 0 are not available, the most recent prior assessment closest to Day 0 may be substituted in some cases, and unless otherwise specified.

C. Missing Data

For safety and tolerability, missing data, including those not obtained because of death, will be the last value carried forward.

If CTCAE Grade is missing, the event is assumed to be ‘Severe’ (grade 3). If AE relatedness is missing, the event is assumed to be ‘possibly’ related.

When relevant, sections below will address how missing data will be handled for the particular analyses. Otherwise, missing data will not be replaced with imputed values.

D. Display and Imputation Methods for Missing Dates

Every effort will be made to query missing dates. However, partial dates are allowed on the eCRF for Adverse Event (AE) onset and resolution dates (only month and year are required), Concomitant Medication (CM) start and stop dates (only year is required), and Prior and Concurrent Cancer Chemotherapy (PCTHX) start and stop dates (only year is required).

Per protocol, Adverse Events (AEs) are captured in the eCRF commencing with the first dose of IMG-7289 through to the End of Study Visit (scheduled for approximately 28 days post last IMG-7289 dose). For records with missing AE onset day, the following procedure will be employed for use in determining whether the AE is treatment-emergent:

- AE onset dates with missing day will be assumed to occur on the first day of the non-missing month, except for AEs occurring in the first month of dosing, in which case the date will be the first day of dosing.

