Additionally, if for some reason the start date of an AE is partially or completely missing and the end date of the AE does not indicate that the AE occurred prior to the first dose of IMG-7289, then the determination of treatment-emergent status will be based on the following:

- If the start date is completely missing, then the AE is treatment-emergent.
- If the start year is the same as the year of the first dose of study drug and the start month is the same or after the month of the first dose of study drug, then the AE is treatment-emergent.
- If the start year is after the year of the first dose of study drug, then the AE is treatment emergent.

For records with a missing CM or PCTHX start and/or stop day or month, the following procedure will be employed for use in determining whether the therapy (i.e., medication or chemotherapy) is prior or concomitant/concurrent:

- Therapy start dates with a missing day and non-missing month will be assumed to occur on the *first* day of the non-missing month, except for therapies occurring in the first month of dosing, in which case the date will be the first day of dosing.

- Therapy start dates with a missing day and month will be assumed to occur on the *first* day of the non-missing year (i.e., January 1), except for medications occurring in the first year of dosing, in which case the date will be the first day of dosing.
- Therapies that are not marked as ongoing, and have a stop date with a missing day and non-missing month will be assumed to occur on the *last* day of the non-missing month.
- Therapies that are not marked as ongoing, and have a stop date with a missing day and month will be assumed to occur on the *last* day of the non-missing year (i.e. December 31).

For the listings, AE, CM and PCTHX dates will be listed as collected in the eCRF.

All other data will be reported as they are collected. No imputation methods will be used to replace missing data unless otherwise stated in this document.

Partial transfusion start dates are not permitted, and thus assumptions should not be needed to determine if the transfusion was prior to the first dose of IMG-7289.

E. Multiple Study Centers

There will be no adjustment for multiple study centers in the analysis.

F. Covariate Adjustment in Primary Analysis

There will be no adjustment in the analysis for covariates.

G. Sample Size Reassessment

No sample size reassessment is planned for this study.

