Prior medication is defined as any medication with a stop date prior to the date of first dose of IMG-7289. Concomitant medications are defined as medications or therapies with a start date on or after the first dose of IMG-7289. Medications may be flagged as both prior and concomitant if the start date is prior to the date of the first dose of IMG-7289 and the medication continued after the first dose of IMG-7289. The medications will be coded using the most updated version of WHO Drug at the time of study initiation (up-versioning will not occur) and will be listed by cohort and by patient. The number (%) of patients using prior, prior and concomitant, and concomitant medications will be summarized.

G. Prior and Concomitant Transfusions

Prior transfusions are defined as those with a transfusion start date from the 15 days prior to Screening up to the first IMG-7289 dose. Concomitant transfusions are defined as those with a transfusion start date on or after the date of the first IMG-7289 dose. Prior and concomitant transfusions will be listed and summarized.

H. Prior and Concurrent Cancer Chemotherapy

Prior chemotherapy is defined as therapy that has ended before the first IMG-7289 dose. Concurrent cancer chemotherapy is defined as having a cancer chemotherapy start date on or after the date of the first IMG-7289 dose. Prior and concurrent chemotherapy will be listed.

X. Pharmacokinetic Analyses

Pharmacokinetic data are not within the scope of this SAP. Analysis details are provided in the protocol and in a separate Pharmacokinetic Analysis Plan.

XI. References

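### The SAP's partial-date rule for therapies does not check the stop date, so a therapy known to have ended before first dose can be given a start after its stop and flagged concomitant

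*SAP*

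**What the plan says.** SAP VI.D gives rules for incomplete start and stop dates of concomitant medications and of prior and concurrent chemotherapy. Their stated use is to decide whether a therapy is prior or concomitant/concurrent. The eCRF requires only the year for these dates.

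- **Start, day and month missing:** the default is "Therapy start dates with a missing day and month will be assumed to occur on the *first* day of the non-missing year". The exception for the dosing year then reads "except for medications occurring in the first year of dosing, in which case the date will be the first day of dosing".
- **Start, day missing only:** the first of the recorded month, "except for therapies occurring in the first month of dosing, in which case the date will be the first day of dosing".
- **Stop, therapy not marked ongoing:** a "stop date with a missing day and month will be assumed to occur on the *last* day of the non-missing year"; with only the day missing, the last day of the month is used.

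SAP IX.F then classifies medications:

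- The stop date decides the first category: "Prior medication is defined as any medication with a stop date prior to the date of first dose of IMG-7289".
- The start date alone decides the second: "Concomitant medications are defined as medications or therapies with a start date on or after the first dose of IMG-7289".
- A medication may carry both flags if it began before first dose and continued after it.

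SAP IX.H defines concurrent chemotherapy by start date alone, on or after first dose. IX.F plans counts and percentages of patients in the three medication categories. IX.H plans only a listing.

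**The concern.** Each exception in VI.D applies to any partial start in the dosing year or dosing month. Neither asks whether the therapy had already ended. The concomitant definition uses only the start date, so a start moved to the day of first dose always satisfies it, even when the recorded stop shows that the drug was finished earlier.

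The same section already has the missing safeguard for adverse events. Its supplementary rule for partially or completely missing AE start dates assigns treatment-emergent status only if the end date does not place the event before first dose. The therapy rules have no counterpart.

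At stake is the accuracy of a planned descriptive table and of a label in a listing. A program that follows the SAP as written would also produce derived records whose start is later than their stop.

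**Working it through.** The plan states no figure to reproduce here, so the check is a literal application of the rules.

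**Inputs.** Start and stop imputation from SAP VI.D; prior = stop before first dose, and concomitant = start on or after first dose, from SAP IX.F. For illustration only, first dose is assumed to be 15 July 2020.

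| Recorded start | Recorded stop | Imputed start | Imputed stop | Result under the SAP |
|---|---|---|---|---|
| 2020 | 10 Jun 2020 | 15 Jul 2020 | 10 Jun 2020 | start after stop; prior and concomitant |
| 2020 | Jun 2020 | 15 Jul 2020 | 30 Jun 2020 | start after stop; prior and concomitant |
| Jul 2020 | 10 Jul 2020 | 15 Jul 2020 | 10 Jul 2020 | start after stop; prior and concomitant |
| 2020 | 2020 | 15 Jul 2020 | 31 Dec 2020 | concomitant only |
| 2019 | 10 Jun 2020 | 1 Jan 2019 | 10 Jun 2020 | prior only |
| Feb 2020 | 10 Jun 2020 | 1 Feb 2020 | 10 Jun 2020 | prior only |

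The first three rows show the defect. The last two show its boundary: a start in an earlier year, or in a known month before the dosing month, is handled correctly.

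**General case.** Let F be first dose, S the imputed start and E the stop, with a year-only start in the dosing year and E < F.

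- The rule gives S = F, so S ≥ F and the concomitant definition is met.
- E < F, so the prior definition is met.
- S = F > E, so the interval is impossible.

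In a 366-day year the number of pairs with a stop day earlier than the first-dose day is 366 × 365 / 2 = 66,795. Enumerating them gave 66,795 of 66,795 flagged both prior and concomitant, each with start after stop. This is the result by construction. It measures how completely the rule fails in this situation, not how often the situation arises.

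**Against the SAP's own both-flags condition.** IX.F allows both flags for a medication that started before first dose and continued after it. On its imputed dates, an affected record has neither property.

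**With a stop-date condition.** If the first-dose substitution is skipped when the recorded or imputed stop precedes first dose, the first three rows become prior only, with starts of 1 January, 1 January and 1 July 2020. The enumeration gives 0 of 66,795 flagged concomitant. The fourth row does not change.

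**The case against.** **Treating an unknown start as concomitant is a normal conservative convention.** This stands where the stop is unknown, or falls on or after first dose. It also covers a therapy with start and stop both recorded only as the dosing year: a reader might call its concomitant-only result an error, but the recorded dates cannot show that it ended before dosing. The convention does not reach a therapy whose recorded or imputed stop is before first dose.

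**The prior flag is not lost.** Correct. With a stop before first dose the record still counts as prior. The error is an added, contradictory concomitant flag, which a check for start after stop would detect.

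**Few records may be involved.** This is fair. The SAP promises efforts to query missing dates. Apart from disease-treatment history, Protocol 9.2.1 collects concomitant medication plus anything used in the 15 days before Screening. Screening opens at Day -28, so routine medications are requested back to about Day -43 (28 + 15). Querying reduces partial dates but does not remove them, because the eCRF accepts them.

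**The AE comparison is not exact.** The basic AE rule for a missing onset day also uses a first-month exception and states no end-date check; the check is in the supplementary paragraph. The comparison shows that the condition is already known to this SAP, not that every AE rule carries it.

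**A reader might infer that the spleen results are compromised.** Inclusion criterion 10 requires patients to "Have discontinued all previous therapies for MPNs including ruxolitinib", so correctly washed-out patients might seem to appear on confounding or prohibited therapy. The documents do not support this step. The visible spleen analyses in SAP VIII.A are descriptive statistics and t-tests. There is no covariate adjustment, the only analysis population is the Safety population, and no visible rule excludes or censors by concomitant therapy. Nor does the visible text say on which form earlier myelofibrosis therapy is recorded; prior disease treatment has its own summary, with redacted detail.

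**Conclusion.** The defect is real and minor. Under SAP VI.D with IX.F and IX.H, any therapy whose start is known only to the dosing year, or only to the dosing month, and whose recorded or imputed stop precedes first dose is given a start after its stop and meets both the prior and the concomitant or concurrent definitions. Counts in the medication summary, and the concurrent label for chemotherapy, may therefore be wrong for an unknown number of records.

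The conclusion rests on reading the rules literally. One wording point is open: the year-level exception speaks of medications and the month-level exception of therapies, so it is unclear whether the year-level exception covers chemotherapy. The effect is limited in other ways too. Chemotherapy is only listed, and listings show medication and chemotherapy dates as collected, so the raw information stays visible. No visible spleen or adverse event analysis is affected.

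**What to change.** In SAP VI.D, make both start-date exceptions conditional: use the first-dose date only when the therapy is ongoing, or when its stop date, recorded or imputed under the existing stop-date rules, is on or after first dose. Otherwise use 1 January of the recorded year or the first of the recorded month. Use one term, therapies or medications, in both exceptions so that their application to chemotherapy is clear.

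Leave therapies with both dates known only to the dosing year as concomitant, and say that this is a convention. Capping an incomplete stop date at the day before first dose would be a preference, not a correction, and is not needed.

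The cost is a sentence or two in the SAP and a line of code. No data collection changes.

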- Changes in physical examinations, vital signs and laboratory values will also be evaluated and assessed from Screening/Baseline until End of Study (EoS)/End of Treatment (ET). Information on the timing of these assessments is presented in the schedule of assessment. **CCI**

CCI

- Pharmacokinetic (PK) parameters will be determined using serial blood sampling at specified time-points to determine PK effects of IMG-7289 (Phase 1/2a only). Non-compartmental methods of analysis will be used to determine PK parameters following oral dosing of patients. **CCI**

CCI

[figure not shown]
CCI

- Reduction in spleen volume will be assessed based on spleen volume measured by MRI (or CT scan where applicable) from Day 0, and spleen size measured by palpation from Baseline to each visit where the variables are measured.

CCI

[figure not shown]

IV. Study Design

A. Design Overview

This is a multi-center, open-label study evaluating the safety, tolerability, steady-state pharmacokinetics and pharmacodynamics of IMG-7289 administered orally once daily in patients with myelofibrosis (MF).

The therapeutic goal for the treatment of MF is to inhibit the activity of LSD1 in haematopoietic cells for only a fraction of the 24-hour dosing cycle sufficient to reduce platelets to a safe level while inhibiting to the greatest extent possible the production, by megakaryocytes, of cytokines and growth factors that drive bone marrow fibrogenesis and symptoms. Considerations for a safe and therapeutic starting dose included chronic toxicology studies, in conjunction with clinical experience of the patients who have received IMG-7289 to date in both IMG-7289-CTP-101 and -102. CCI

CCI

This study initiated as a Phase 1/2a study, assessing the safety of the starting dose, an 85-day duration of treatment, and the pharmacokinetic and pharmacodynamic effects of IMG-7289, with transition to a Phase 2b study including implementation of changes supported by the Phase 1/2a data.

This study consists of two treatment periods: The Initial Treatment Period (ITP), followed by the Additional Treatment Period (ATP); the ATP is iterative, and allows patients to continue treatment if they derive clinical benefit (defined as not meeting progressive disease criteria as per protocol Section **Erreur ! Source du renvoi introuvable.**) and safety tolerating IMG-7289 as determined by the Principal Investigator

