Patients enrolled in the Phase 1/2a portion of study are treated in the ITP daily for 85 days; if qualified, they may continue to the ATP after a brief washout period, and be treated daily for an additional 85 days. Patients enrolled in the Phase 2b portion of study are treated in the ITP daily for 169 days; if qualified,

they may continue directly to the ATP with no washout period, and be treated daily for an additional 169 days.

All patients will undergo follow-up period visits, including an End-of-Treatment (EoT) visit on the day of last dose or as soon as possible thereafter, a pre-End-of-Study (EoS) visit approximately 14 days post last dose, and an End-of-Study (EoS) visit approximately 28 days post last dose. Patients that do not enter the Additional Treatment Period, or discontinue early, will undergo follow-up, beginning with an EoT visit.

Patients will be followed closely throughout the study for both Adverse Events (AEs) and signs of toxicity by frequent monitoring of clinical signs and symptoms and by peripheral blood and urine analyses. Pharmacodynamic effects will be closely monitored by frequent haematology assessments of peripheral blood, and requisite bone marrow aspirates and biopsies. Throughout dosing, transfusions may be administered if needed in accordance with standard institutional guidelines.

B. Study Population

The patient population will consist of men and women age 18 or older who have been diagnosed with intermediate-1, intermediate -2 or high-risk primary myelofibrosis (PMF), post-polycythaemia vera myelofibrosis (PPV-MF), or post-essential thrombocythaemia myelofibrosis (PET-MF). Eligible patients who have signed informed consent must have had no prior treatments within a specified period of time and met pre-specified laboratory values for selected parameters, in addition to multiple other required eligibility criteria.

C. Sample Size Predictions

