Approximately seventy-five (75) MF patients are expected to be enrolled and treated in the study and a minimum of 45 patients are required to complete the entirety of the Initial Treatment Period (including MRI/CT). This study is designed to make an assessment of the safety, tolerability, and pharmacokinetics of the capsule formulation of IMG-7289. The Phase 1/2a portion of the study was planned for a minimum of 15 patients; with 18 enrolled and treated patients, the Phase 1/2a portion of the study is sufficiently powered to determine mean pharmacokinetic parameters. Given that all pharmacodynamic (PD) metrics are exploratory in nature, the study is not powered to make statements about the statistical significance of any changes observed.

D. Treatment Randomization

This is not a randomized study.

CCI

CC

V. Interventions

A. Clinical Trial Material

The drug product is IMG-7289, a bis-tosylate salt. The free base of IMG-7289 is the active moiety. IMG-7289 will be supplied in capsules of multiple strengths. These strengths, based on IMG-7289 free base, i.e. the active substance, may include: 1 mg, 5 mg, 10 mg, 25 mg, and 50 mg. At Phase 2b, 1 mg capsules are not provided.

B. Study Procedures

Patients will undergo procedures described in protocol Section 9 to assess the study drug safety, pharmacodynamics, and pharmacokinetics in order to achieve the study objectives.

VI. General Analytical Considerations

The statistical analyses will be reported using summary tables, figures, and data listings. Unless otherwise noted, all statistical testing will be two-sided with significance being $p < 0.05$. Continuous variables will be summarized with means, standard deviations, medians, minimums, and maximums. Categorical variables will be summarized by counts and by percentage of patients in corresponding categories. As appropriate and where specified, continuous and categorical variables will be evaluated using the paired t-test, Kruskal-Wallis, Wilcoxon rank sum, Sign rank test, Fisher's exact, or χ^2 tests to assess the significance of differences in haematologic, pharmacodynamics markers, and response. As appropriate and where specified, summary tables will be presented by the type of disease within starting dose, with an "All Patients" summary. Refer to section VI.K for details.

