If sufficient patients within a phase and cohort have visits that are performed off-schedule, and there is concern that summary by designated visit within period will be misleading due to comparison of assessments that have not had comparable treatment duration within that period, then visit windowing may be utilized for data summarization. In that case, visit windows will be defined by establishing the expected schedule for the dose/cohort, and establishing boundaries for each window as the midpoint between the previous expected visit day and the next expected visit day. Assessments will be slotted for summarization according to the visit windows, rather than the visit designated in the eCRF. If more than one assessment occurs within a particular window, then the assessment closest to the expected visit day will be used. If more than one such assessment exists, then the assessment whose visit designation in EDC is closest to the expected visit designation will be used. If windowing is applied for a given type of assessment, this will be indicated in the footnote of the summary table and the corresponding listing, and the listing will indicate both the visit designation from EDC and the visit window in which the assessment is included.

This methodology may be applied to summaries of laboratory data, vital signs data, and/or symptom scores. As assessment schedules may differ for these assessments, windows may be parameter type-specific.

K. Analysis Populations

Only the Safety population will be considered as analysis population for performing the various analyses. All enrolled patients who received at least one dose of IMG-7289 will be included in the Safety population.

Patients having no post-baseline disease assessment will be defined as NE (not evaluable).

L. Subgroups of Analysis Populations

The summaries and listings will be separated by the starting dose, and type of disease within starting dose. Summaries will include an “All Patients” category for each starting dose, as well as an “All Patients” category for the entire set of patients in the analysis set.

Categories for starting dose are: Phase 1/2a - 0.25 mg/kg/d (amendments 1, 2 and 3); Phase 2b - 0.5 mg/kg/d (amendments 4, 5); and Phase 2b - 0.6 mg/kg/d (amendment 6).

Categories for type of disease are: primary myelofibrosis (PMF), post-polycythaemia vera myelofibrosis (PPV-MF), or post-essential thrombocythaemia myelofibrosis (PET-MF) within starting dose category.

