VIII. Efficacy Analyses

A. Primary Analysis

1. Spleen Volume

Spleen volume (mL) will be measured by MRI (or CT scan where applicable) from Day 0. Descriptive statistics will be presented for actual spleen volume, change from baseline, and percentage change from baseline by visit; and for maximum percentage change from baseline, minimum percentage change from baseline, and best percentage change from baseline will be presented. The best percentage change from baseline is defined as the maximum percentage decrease or the minimum percentage increase if there is no decrease in a patient during treatment.

In addition, an analysis of mean spleen volume will be performed. The mean and its 95% confidence interval (CI) will be presented for the spleen volume (mL), change from baseline, and percentage change from baseline at each visit; and for the best percentage change from baseline. P-value for test to assess change from baseline at each visit will be calculated using paired t-test. P-value for test to assess percentage change from baseline at each visit and the best percentage change from baseline will be calculated using one sample t-test with the hypothesis that the percentage change is 0.

2. Spleen Size

Spleen size (cm) will be measured by palpation at each visit. Descriptive statistics will be presented for actual spleen size, change from baseline, and percentage change from baseline by visit; and for maximum percentage change from baseline, minimum percentage change from baseline, and best percentage change from baseline will be presented. The best percentage change from baseline is defined as the maximum percentage decrease or the minimum percentage increase if there is no decrease in a patient during treatment.

In addition, an analysis of mean spleen size will be performed. The mean and its 95% confidence interval (CI) will be presented for the spleen size (cm), change from baseline, and percentage change from baseline at each visit; and for the best percentage change from baseline. P-value for test to assess change from baseline at each visit will be calculated using paired t-test. P-value for test to assess percentage change from baseline at each visit and the best percentage change from baseline will be calculated using one sample t-test with the hypothesis that the percentage change is 0.

CCI

CCI

CCI

CCI

CCI

[figure not shown]

IX. Safety Analyses

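### The by-visit Day 168 spleen volume analysis omits Phase 2b patients stopped earlier for confirmed splenic growth, and no visible analysis estimates end-of-ITP change for all treated Phase 2b patients

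*SAP*

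**What the plan says.** SAP VIII.A.1 presents spleen volume, change and percentage change at each visit as a mean with 95% confidence interval. On the tests it says: "P-value for test to assess change from baseline at each visit will be calculated using paired t-test". Percentage change gets a one-sample t-test against 0. Maximum, minimum and best percentage change are also summarised, and best change has its own interval and test.

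SAP VI.C carries the last value forward for safety and tolerability only, and leaves other cases to the individual sections: "Otherwise, missing data will not be replaced with imputed values". VIII.A.1 adds no rule. Optional visit windowing in SAP VI.J does not name imaging: "This methodology may be applied to summaries of laboratory data, vital signs data, and/or symptom scores".

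Protocol 5.1.1 schedules ITP scans at Days 84 and 168, after the Day 0 scan. Under Protocol 6.8, patients not deriving clinical benefit, which includes those meeting progressive disease criteria, discontinue and go to End of Treatment (EoT). Protocol 16.7 requires a palpation threshold plus imaging confirmation of at least 25% volume growth for splenic progression. Protocol 9.6.1 asks for an EoT scan unless one was done in the prior 5 weeks, and lets the Day 168 visit stand in for EoT in patients who complete a treatment period and leave.

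The cohorts differ in length: "Patients enrolled in the Phase 1/2a portion of study are treated in the ITP daily for 85 days", against 169 days in Phase 2b (SAP IV.A). SAP IV.C puts about 75 patients in the study, 18 of them in Phase 1/2a, and requires at least 45 to complete the ITP including imaging. Protocol 6.4 says non-completers may or may not be replaced.

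**The concern.** A paired or one-sample t-test at Day 168 is an observed-case analysis. That is harmless if the missing scans are unrelated to spleen volume. Here one route to a missing scan is growth of the spleen itself. A patient with confirmed splenic progression at, say, Day 84 stops, is followed for about 28 days after the last dose, and has no Day 168 scan. The Day 168 mean then describes patients who reached Day 168 rather than all treated Phase 2b patients, and this part of the missingness favours the drug. Day 168 is the last scheduled ITP scan in Phase 2b, so readers are likely to take its mean as the end-of-ITP result. What is at stake is an estimate that may flatter, not a wrong formal decision.

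**Working it through.** **From the documents.** Phase 2b patients: 75 - 18 = 57. Non-completers that the completion minimum would tolerate: 75 - 45 = 30, and 30/75 = 40%. That minimum covers the 85-day and 169-day cohorts together. It is a floor, not a forecast of missing Day 168 scans among the 57. No SD, correlation, effect size or stop rate is given for spleen volume, so there is no planned figure to reproduce.

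**Assumed.** Percentage change is normal with mean m at every visit and SD 20 points. The Day 84 to Day 168 correlation is 0.7. A patient with growth of at least 25% at the deciding scan stops with probability p.

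**Formula.** Let z = (25 - m)/20, P = 1 - Φ(z) and T = 20 × φ(z), and let c be the correlation of the deciding scan with Day 168. Removing the stopped patients shifts the Day 168 mean by

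shift = -c × p × T / (1 - p × P).

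**Half of Day 84 growers stop (p = 0.5, c = 0.7).**
- m = 0: z = 1.25, P = 0.1056, T = 3.653. Expected stops 57 × 0.5 × 0.1056 = 3.0. Shift = -0.7 × 1.827/0.947 = -1.35.
- m = -10: z = 1.75, P = 0.0401, T = 1.726. Expected stops 57 × 0.5 × 0.0401 = 1.1. Shift = -0.7 × 0.863/0.980 = -0.62.

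Simulation (20,000 runs per case, two-sided test at 0.05) agrees: -1.37 and -0.61.

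| Deciding scan | Share stopping | Shift, m = 0 | Rejection, m = 0 | Shift, m = -10 | Rejection, m = -10 |
|---|---|---|---|---|---|
| Day 84 | quarter | -0.67 | 5.7% | -0.28 | 97.0% |
| Day 84 | half | -1.37 | 7.5% | -0.61 | 97.8% |
| Day 84 | all | -2.88 | 19.0% | -1.26 | 99.0% |
| about Day 126 | quarter | -0.81 | 5.5% | -0.40 | 97.4% |
| about Day 126 | half | -1.62 | 9.2% | -0.75 | 98.3% |
| about Day 126 | all | -3.41 | 26.3% | -1.50 | 99.5% |

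The half-stop, Day 84 rejection rate varied between 7.5% and 8.1% across runs. The Day 126 rows need an off-schedule scan. The rows where all stop ignore the palpation threshold.

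**Sensitivity to inputs.** With half stopping, SD 15 to 25, correlation 0.5 to 0.85 and either timing, the shift runs from -0.4 to -3.0 points at m = 0 and from -0.1 to -1.8 at m = -10.

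**Other stops.** Start from half of Day 84 growers stopping. At m = 0, 12 further random stops leave the shift at -1.4. If the further stops come from the half shrinking most, 6 reduce it to -0.2 and 9 turn it to +0.6. At m = -10, 3 such stops bring it to about 0.

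**Candidate repairs, same model.**
- A likelihood estimate using Days 84 and 168 is within 0.05 points of the truth when stopping depends on the Day 84 scan. It keeps -0.1 to -1.3 points when stopping depends on a Day 126 value that the model does not see.
- Using the last scan of each stopped patient shifts the mean by (1 - c) × p × T. At m = 0 with half stopping at Day 84 this is 0.3 × 0.5 × 3.653 = +0.55. Over the table's cases it runs from about +0.1 to +1.1.

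**The case against.** The strongest reply is that the SAP never claims an end-of-ITP estimate. SAP III.A names no primary visit. It assesses volume from Day 0, and "spleen size measured by palpation from Baseline to each visit where the variables are measured". Patients who progress are not lost from every summary either. They are in the Day 84 row if scanned then, in any EoT row, and in the maximum, minimum and best change. Patients found to be progressing at Day 168 are scanned and counted there. All of this stands. It does not fill the gap: Day 84 is an earlier time, an EoT row would hold mainly early stops, and the extremes range over all treatment, with best change taking each patient's most favourable value.

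Several blocks after VIII.A.2 and the disposition list are redacted, and the table shells are a separate document. An end-of-ITP analysis, or the reasons for missing scans, may already be there. The point is limited to visible text.

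The study is also stated not to be powered for significance, and no success rule is visible. That limits the consequence, but intervals and p-values are still planned.

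A reader might infer that the Day 168 result is biased toward benefit overall. The documents do not support that, because stops for toxicity or other reasons have no known direction and could cancel or reverse the shift. Nor do they support expecting 40% dropout, reading Protocol 6.4 as a bar on replacement, or assuming that EoT scans from the ITP and later periods would be pooled, since SAP VI.J presents visits by treatment period.

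**Conclusion.** The point holds as a limited one. On the visible text, the Day 168 analysis in the 169-day cohorts is observed-case, one cause of missing scans is growth in the primary variable, and no end-of-ITP estimate for all treated Phase 2b patients is shown. That component biases toward shrinkage; the net sign is not established.

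The central illustration is about -1.4 points with rejection about 8% at true change 0, and about -0.6 points at true change -10. It rests on n = 57, SD 20, correlation 0.7 and half of Day 84 growers stopping, none of which but n comes from the documents. The largest tabulated values, -3.4 points and 26%, should not be taken as likely. They need every grower to stop regardless of palpation and an off-schedule scan, whereas the visible off-schedule triggers are EoT, early termination and suspected relapse, and Protocol 9.5 restricts relapse to patients who have first responded.

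This is a worthwhile supportive-analysis improvement, not a flaw that undermines the study.

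**What to change.** Keep the by-visit tests. If no equivalent exists in the redacted text or shells, add the following to SAP VIII.A.1 for the 169-day ITP cohorts before database lock.

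- **Mixed model for repeated measures** of percentage change in spleen volume at Days 84 and 168, with visit as the only fixed effect and unstructured covariance. It has no covariates, so SAP VI.F needs no exception. Use all treated patients with a baseline and at least one post-baseline scan. A patient whose only such scan is an off-schedule EoT or early-termination scan contributes through the next item.
- **Sensitivity analysis** using the Day 168 scan or, for early stops, the EoT or early-termination scan, or the last on-treatment ITP scan where no such scan was required or obtained. State that it is a different estimand, with mixed treatment durations, and may err slightly toward a less favourable value.
- **Accounting at each visit**: the number scanned and the reasons for missing scans, with confirmed splenic progression as its own category.

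No new scans are needed. The costs are SAP wording, modest programming, a model that assumes missingness depends only on observed scans, and a possibly slightly less favourable estimate.
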